#### 11.1.2.4 Statistical Methods

Endpoint analysis will be performed on subjects that undergo an EMPOWER PG implant procedure, including subjects that do not have the EMPOWER PG successfully implanted (i.e., both implant and attempt subjects), using two different cohorts. The CE Mark cohort will consist of the minimum number of subjects required to evaluate this endpoint - 112 subjects who undergo an EMPOWER PG implant procedure and have been followed for 12 months. The FDA Post-Market 1 cohort will consist of all subject enrollments who undergo an EMPOWER PG implant procedure and are followed for 12 months.

The Major EMPOWER MPS System- and Procedure-related CFR from the date of the EMPOWER PG implant procedure through 365 days post implant will be calculated using Kaplan-Meier methodology.

The 97.5% one-sided lower pointwise confidence limit of the Major EMPOWER MPS System- and Procedure-related CFR will be calculated via log-log methodology and compared to the performance goal of 81%. If the lower confidence limit exceeds 81%, the null hypothesis will be rejected.

The Kaplan-Meier methodology was chosen for this endpoint to utilize all available data for each subject. To assess the robustness of this analysis method and the potential impact missing data could have had on the analysis results, a tipping point analysis will be conducted that will include subjects with the EMPOWER PG implanted and the attempted subjects. The tipping point analysis will assign each subject with missing data as either having or not having a Major EMPOWER MPS System- and Procedure-related Complication. All possible combinations of these subjects' data will be evaluated along with the actual observed data to find the point, if any, at which the endpoint is failed.

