#### 11.1.3 Secondary Safety Endpoint: All-Cause Survival from Implant through 2 Years Post-Implant

The Secondary Safety Endpoint will be assessed for all implant subjects. Safety will be confirmed by evaluating the 2-Year all-cause survival rate post implant. Deaths due to any reason will count against this endpoint. Data from this endpoint will be used to evaluate the longer-term safety of the EMPOWER PG for the purposes of obtaining CMS approval and Medicare reimbursement. This analysis will be performed when all implanted subjects have been followed for a minimum of 730 days. In order to control the overall study Type I error rate, this endpoint will only be evaluated if Safety Endpoint 1,the primary effectiveness endpoints, and the Secondary Effectiveness endpoint are successful.

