#### 11.1.3.2 Sample Size

A sample size of 123 implanted subjects followed for 2 years is required to evaluate the Secondary Safety Endpoint. This sample size was calculated based on a one-sided normal approximation for a single binomial proportion, using SAS Version 9.4 with the following assumptions:

- Performance goal = 85%
- Significance level = 2.5% one-sided
- Power = 80%

Given an expected attrition rate of 40%, 275 subjects are needed, which is less than the 300 enrolled subjects. This means that the overall study sample size is not being driven by this endpoint.

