#### 11.1.3.3 Statistical Methods

Endpoint analysis will be performed on all implanted subjects.

The survival rate from the implant through 730 days post-implant will be calculated using Kaplan-Meier methodology. Deaths for any reason will count as an event for this endpoint. The 5% one-sided lower pointwise confidence limit of the survival rate will be calculated via log-log methodology and compared to the performance goal of 85%. If the lower confidence limit exceeds 85%, the null hypothesis will be rejected.

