# 11.1.5.3 Statistical Methods

The analysis for this endpoint will be performed once, either in conjunction with the interim analysis of Safety Endpoint 1, if the analysis of Safety Endpoint 1 is successful in rejecting the null hypothesis, or at the time of the final analysis of Safety Endpoint 1. Two groups of subjects will be included in the endpoint evaluation: (1) PMA Sample cohort subjects with an EMPOWER PG PCT measurement taken at the 6 Month Visit (with a 0.4 ms pulse width), and (2) PMA Sample cohort subjects with a Major EMPOWER MPS System- and Procedure-related Complication between implant and 6 months due to an elevated threshold. The number of responders (PCT at 6 Month Visit  $\leq 2.0$  [contact] ms) divided by the total number of subjects included in the endpoint evaluation will be calculated. The one-sided 2.5% binomial exact lower confidence limit will be calculated and compared to the performance goal of 80%. If the lower confidence limit exceeds 80%, the null hypothesis will be rejected.

To assess the potential impact missing data could have had on the analysis results, a tipping point analysis will be conducted that will include subjects with the EMPOWER PG implanted. The tipping point analysis will assign each subject with missing data as

MODULAR ATP

Page 89 of 148

either being a PCT responder or a PCT non-responder. All possible combinations of these subjects' data will be evaluated along with the actual observed data to find the point, if any, at which the endpoint is failed.

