# 11.5 General Statistical Methods

# 11.5.1 Study Success Criteria and Control of Type I Error

The study will be considered successful if Safety Endpoint 1 and all primary effectiveness endpoints are passed.

Safety Endpoint 1 and the primary effectiveness endpoints can be tested at the significance level of 2.5% while still maintaining the overall type I error level at no greater than 2.5%. This follows the methodology of the Intersection-Union Test (IUT). Additionally, in order to control the overall type I error level a gating approach will be employed. The Secondary Effectiveness Endpoint and Secondary Safety Endpoint will only be evaluated if Safety Endpoint 1 and the primary effectiveness endpoints are successful. The secondary endpoints will be tested in the following order:

- Secondary Effectiveness Endpoint
- Secondary Safety Endpoint, which will only be tested if Seconardy Effectiveness Endpoint is successful.

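### The 2-year survival endpoint is planned at one-sided 2.5% but decided with a 5% one-sided limit, so the last gated test runs above the 2.5% level

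*Protocol*

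**What the plan says.** Two adjacent subsections of the protocol give different levels for the same test.

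- Section 11.1.3.2, sizing: "Significance level = 2.5% one-sided", with 80% power, a performance goal of 85% and 123 implanted subjects followed for 2 years. It adds: "Given an expected attrition rate of 40%, 275 subjects are needed".
- Section 11.1.3.3, decision: "The 5% one-sided lower pointwise confidence limit of the survival rate will be calculated via log-log methodology". The null hypothesis is rejected if that limit is above 85%.

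Section 11.1.3 explains why the endpoint is gated: "In order to control the overall study Type I error rate, this endpoint will only be evaluated if Safety Endpoint 1" and the effectiveness endpoints succeed. Section 11.5.1 says Safety Endpoint 1 and the primary effectiveness endpoints can each be tested at 2.5% "while still maintaining the overall type I error level at no greater than 2.5"%. It then says that "in order to control the overall type I error level a gating approach will be employed" for the two secondary endpoints, with this one last.

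Elsewhere the protocol labels limits in two ways. One is by coverage: Section 11.1.2.4 has "The 97.5% one-sided lower pointwise confidence limit of the Major EMPOWER MPS System- and Procedure-related CFR will be calculated via log-log methodology", and Sections 11.1.1.3 and 11.1.4.3 use 98.8%, 98.1% and 97.5%. The other is by alpha: Section 11.1.5.3 has "The one-sided 2.5% binomial exact lower confidence limit will be calculated and compared to the performance goal of 80"%. The SAP text gives no level for the survival endpoint.

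**The concern.** An analyst who follows Section 11.1.3.3 runs the test at twice the planned one-sided level. In a fixed-sequence gate each step has to be tested at the family level. If the last step is run at 5%, the chance of a false claim can reach about 5% when the earlier endpoints are truly effective and only the survival null is true.

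Section 11.1.3 says this endpoint is meant to support CMS approval and Medicare reimbursement. A survival result that misses at the planned level could therefore be reported as a success. Correcting the level after the data are known would look post hoc.

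**Working it through.** **1. The plan's own sample size.** The inputs are goal p0 = 0.85, one-sided alpha 0.025 and power 0.80 (Section 11.1.3.2). The available text does not give the expected survival p1, so 123 cannot be reproduced directly. The formula is

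n = [z(1−α)·√(p0·q0) + z(power)·√(p1·q1)]² / (p1 − p0)², then with continuity correction n′ = (n/4)·[1 + √(1 + 2/(n·|p1 − p0|))]².

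The corrected form reproduces the other endpoints from the synopsis inputs: Safety Endpoint 2 gives 111.9 (stated 112), Primary Effectiveness 1 gives 151.3 (152) and Primary Effectiveness 2 gives 56.7 (57). Solving for the survival that yields 123:

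| alpha | implied p1, uncorrected | implied p1, corrected |
|---|---|---|
| 2.5% | 93.2% | 93.6% |
| 5% | 92.3% | 92.7% |

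All four are plausible, so 123 does not show which alpha was used.

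**2. What the 5% can mean.** If it is coverage, z is −1.645. With 34 deaths in 180, S = 146/180 = 0.8111 and the log-log limit is 0.8540, which is above 0.85. An observed survival of 81.1% would pass an 85% goal, so this reading is unusable. That leaves alpha of 5%, the labelling style of Section 11.1.5.3.

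**3. The decision rule, complete follow-up.** With d deaths among n, S = 1 − d/n, se = √[d/(n(n − d))] / |ln S|, limit = S^exp(z·se). Success means limit > 0.85. Type I error is P(X ≤ largest passing d), with X ~ Bin(n, 0.15).

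Worked case n = 180 (300 × 0.60, enrolment less 40% attrition):

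- d = 17: S = 0.9056, se = 0.2426. The limit is 0.8525 at z = 1.960, so it passes at 2.5%.
- d = 18: S = 0.9000, se = 0.2358. The limit is 0.8460 at z = 1.960 (fails) and 0.8562 at z = 1.645 (passes).
- d = 19: the limit is 0.8498 at z = 1.645 (fails).

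| n | max deaths (error), alpha 2.5% | max deaths (error), alpha 5% |
|---|---|---|
| 123 | 10 (1.69%) | 11 (3.35%) |
| 165 | 15 (1.73%) | 17 (5.19%) |
| 180 | 17 (1.92%) | 18 (3.31%) |
| 205 | 20 (1.84%) | 22 (4.88%) |
| 275 | 29 (2.01%) | 31 (4.59%) |
| 298 | 32 (2.05%) | 34 (4.53%) |

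Over all 178 values of n from 123 to 300, the error is 1.17% to 2.41% at alpha 2.5% and 3.10% to 5.32% at alpha 5%. The boundary moves by one death at 54 values of n and by two at 124.

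**4. With censoring.** The assumptions are exponential death with 85% survival at 2 years, independent exponential dropout of 40% by 2 years, and a Kaplan-Meier estimate with Greenwood variance. For 275 or 300 implanted, separate runs of 20,000 to 40,000 trials gave an error of 2.0% to 2.1% at alpha 2.5% and 4.2% to 4.6% at alpha 5%.

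**5. The attrition figures (a separate, minor point).** 123/0.60 = 205, not 275; and 275 × 0.60 = 165, not 123. The documents do not show which figure is wrong. At an assumed 92.5% survival, 2.5% alpha and 80% power, the corrected formula gives 164.03, so 165, and 165/0.60 = 275. That is suggestive only.

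**The case against.** The strongest reply is that this is a typing slip. The matching sentence for Safety Endpoint 2 is nearly identical and has 97.5%; dropping part of 97.5% or 2.5% leaves 5%. The planning level, the gate and possibly the 275 all point to an intended 2.5% test. That is quite likely, and it supports the proposed correction. It does not remove the problem, because Section 11.1.3.3 is the decision rule and no other text overrides it.

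Second, the 2.5% ceiling in Section 11.5.1 is attached to Safety Endpoint 1 and the primary effectiveness endpoints; the next sentence, on the gate, gives no number. This is correct. Applying 2.5% to the gate is an inference, but it is the only overall level stated and it matches the level in Section 11.1.3.2.

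Third, the consequence is limited. The endpoint is secondary and last, nothing is tested after it, the boundary moves by only one or two deaths, and the excess error arises only if every earlier gated test passes and true survival is 85% or lower. All of this stands. It narrows the scope, but the threshold remains wrong as written. Values slightly above 5%, as at n = 165, also reflect discreteness and the log-log approximation, so the simulated figures with dropout are the better guide.

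**Conclusion.** The concern holds. The level in the decision rule (5%) contradicts the level in the sample-size section (2.5%). Taken literally, it roughly doubles the error of the last gated test: about 4.2% to 4.6% instead of 2.0% to 2.1% with 40% dropout. With complete follow-up, the written rule is above 2.5% at every n from 123 to 300, while a 97.5% limit never is. This rests on reading the written figure as alpha, on taking 2.5% as the level the gate should hold, and, for the censored figures, on exponential death and independent dropout. The study success criterion and enrolment are untouched. Because it is a pre-specified decision threshold with a stated reimbursement use, it should be corrected before the 2-year analysis.

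**What to change.** In Section 11.1.3.3, change the figure in the confidence-limit sentence from 5% to 97.5%, so that it reads like the corresponding sentence for Safety Endpoint 2 in Section 11.1.2.4. As a separate minor correction in Section 11.1.3.2, reconcile 123, 40% and 275 so that the evaluable number divided by 0.60 gives the enrolled number.

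The cost is one sentence and one corrected figure. No patients, visits or procedures are added. Both 205 and 275 are below 300, so the statement that this endpoint does not drive the study size still holds.

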#### 11.1.4 Primary Effectiveness Endpoint 1: Communication Success between the S-ICD and EMPOWER PG at the 6 Month Visit

Primary Effectiveness Endpoint 1 will be assessed at the time of the interim analysis of Safety Endpoint 1 if its null hypothesis is rejected, or at the final analysis if its null hypothesis is not rejected at the interim analysis (refer to **Section 11.3**). The assessment will include subjects who are successfully implanted with both the EMPOWER PG and S-ICD. Effectiveness will be confirmed by evaluating the communication between S-ICD and the EMPOWER PG in four postures: upright, supine, and right and left side. The test unit for this endpoint will be the result from each posture. Communication success will be defined as any evidence of a paced beat during communication testing in a given posture at the initial programmed communication Programmed Telemetry Setting.

#### 11.1.4.1 Hypotheses

The following hypotheses will be used to evaluate Primary Effectiveness Endpoint 1 at the 6 Month Visit:

H0: The communication success rate is  $\leq 88\%$ 

 $H_A$ : The communication success rate is > 88%.

### 11.1.4.2 Sample Size

The sample size estimates were obtained using the normal approximation to the binomial and verified through simulations. The required sample size of 152 tests from a minimum of 38 subjects (220 tests including attrition) was calculated using the following assumptions:

- Performance goal = 88%
- One-sided significance level = 2.5%
- Power = 80%
- Attrition = 30%

The sample size for this study was not determined by this endpoint.

#### 11.1.4.3 Statistical Methods

The analysis for this endpoint will be performed once, either in conjunction with the interim analysis of Safety Endpoint 1, if the analysis of Safety Endpoint 1 is successful in rejecting the null hypothesis, or at the time of the final analysis of Safety Endpoint 1. The analysis for this endpoint will use the communication results taken at the 6 Month Visit and the communication success rate will be calculated using the data from all postures.

A repeated measure logistic regression will be fit with an indicator of communication success of each posture test as the response and subject as the repeated measure in an intercept only model to calculated the adjusted communication success rate and the 97.5% one-sided lower pointwise confidence limit. An unstructured correlation matrix will be used, unless a different structure is found to be more appropriate. The adjusted communication success rate and the 97.5% one-sided lower pointwise confidence limit by converting the intercept estimate and 97.5% one-sided upper pointwise confidence limit from the model previously described into an event rate and corresponding confidence limit. This adjusted 97.5% one-sided lower pointwise confidence limit of the communication success rate will compared to the performance goal of 88%. If the lower confidence limit exceeds 88%, the null hypothesis will be rejected. Please see the Statistical Analysis Plan (SAP) for more specifics. The unadjusted rate and 97.5% one-sided lower pointwise confidence limit and 97.5% one-sided using the one-sided Score methodology will also be presented as sensitivity analysis.

A subject-level evalution of the communication success rate across the four postures is being analyzed as an ancillary objective. See **Section 11.2**.

Missing posture testing data due to missed 6 Month Visits or a missing posture of the 4 tested will be considered missing data. To assess the potential impact missing data could have had on the analysis results, a tipping point analysis will be conducted. The tipping point analysis will assign each missing posture test as either a failure or success. All possible combinations of these posture tests' data will be evaluated along with the actual observed data to find the point, if any, at which the endpoint is failed.

The poolability of the communication success rate will be assessed across postures. As part of this analysis the communication success rate will be presented for each posture, and the poolability will be assessed as outlined in pooling analysis in **Section 11.7.3**.

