Primary Effectiveness 1	Communication Success between the S- ICD and EMPOWER PG at 6 Month Visit	95%	88%	One-Sided Lower Pointwise Confidence Limit	2.5%	80%	152 tests/ 38 subjects	30%	220 tests/55 subjects
Primary Effectiveness 2	The percent of subjects with an adequate EMPOWER pacemaker PCT measurement.	95%	80%	One-Sided Lower Confidence Limit	2.5%	90%	57	30%	82

3	Tab	ole of C	Contents						
1.	Тіті	TITLE PAGE1							
2	Pro	ROTOCOL SYNOPSIS6							
3	Тав	LE OF C	ONTENTS						
4	Inte	RODUCTI	ION 21						
•	4.1	Backg	round						
5	Dev	ICE DES	CDIDTION 24						
5	5 1	mCRN	A Coordinated System 24						
	5.1	Imnla	n e oor unateu system						
	53	Non-I	ntable Study Devices 24						
		5.3.1	Non-Implantable Study Devices Associated with the EMPOWER System						
		5.3.2	Model 3870 Programmer Software Application and Associated Firmware25						
		5.3.3	Non-implantable Study Devices Associated with the S-ICD System 26						
	5.4	Access	ories						
	5.5	Additi	onal Equipment27						
6	STU	dy Obje	CCTIVES AND ENDPOINTS27						
	6.1	Study	Objectives						
	6.2	Study	Endpoints						
	6.3	Safety	Endpoints						
	6.4	Effecti	iveness Endpoints						
	6.5	Ancill	ary Objectives						
	6.6	Study	Rationale						
7	STU	DY DESI	GN						
	7.1	Scale a	and Duration						
	7.2	Justifi	cation for the Study Design32						
8	SUB.	JECT SE	LECTION						
	8.1	Study	Population and Eligibility33						
	8.2	Inclus	ion Criteria34						
	8.3	Exclus	sion Criteria35						

9	Subj	ECT AC	COUNTABILITY	36
	9.1	Point o	f Enrollment	36
	9.2	Subjec	t Status and Classification	36
		9.2.1	Intent	36
		9.2.2	Attempt	36
		9.2.3	Partial Implant	36
		9.2.4	Implant	37
	9.3	Access mCRM	to EMPOWER MPS Programmer Software and S-ICD System 1 Programming	ı 37
	9.4	Strateg	gies for Recruitment and Retention	37
	9.5	Withd	rawal	38
	9.6	Lost-to	o-Follow-up	39
	9.7	End-of	-Study Definition	39
	9.8	End of	Study Action Plan	39
10	STUI	ру Метн	HODS	40
	10.1	Data C	Collection	40
	10.2	Enroll	ment Visit	42
		10.2.1	Informed Consent	42
		10.2.2	Enrollment Data	42
		10.2.3	Enrollment Visit Source Documentation Requirements	43
	10.3	Implan	ıt	44
		10.3.1	Implant of the EMPOWER PG	44
		10.3.2	Implant of the S-ICD	48
		10.3.3	S-ICD Firmware Update	50
		10.3.4	mCRM Coordinated System Imaging and Testing	51
		10.3.5	S-ICD Evaluation	56
		10.3.6	S-ICD System Programming Considerations	56
		10.3.7	mCRM Coordinated System Data and Source Documentation Requirements	56
	10.4	Pre-Di	scharge Visit	57
		10.4.1	EMPOWER PG Evaluation	58

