#### 11.6.3 Pooling Analyses

# 11.6.3.1 Assessment of Pooling Across Communication Test Postures

The poolability of the Primary Effectiveness Endpoint 1 data by communication test postures will be performed to determine whether there are differences among the four postures: upright, supine, and right and left side.

Communication test posture heterogeneity will be assessed by performing fixed effects logistic regression analyses. Communication test posture will be added into the model as a fixed effect. Postures will be deemed to be heterogeneous if the variance of the fixed posture effect is found to significantly differ from zero. A significance level of 15% will be used for the test.

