1 ADDITIONAL INFORMATION

1.1 Sample Code for Adjusted Communication Success Rate

The following is sample code that will provide adjusted estimate of the communication success and 97.5% one-sided lower pointwise confidence limit:

where 'success' is an indicator of success for each communication test in all postures, 'subject' is the subject ID for all subjects that are evaluable for the endpoint, 'comm_success' is the adjusted communication success rate and 'lower_CL' is the 97.5% one-sided lower pointwise confidence limit.

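### Primary Effectiveness Endpoint 1: the unstructured, replaceable working correlation means the rate tested need not be the success rate over all posture tests, and the one-sided error can miss 2.5% in either direction

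*Protocol*

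**What the plan says.** Protocol 11.1.4 makes each posture's result the test unit, in four postures per subject. Protocol 11.1.4.3 says "the communication success rate will be calculated using the data from all postures". It then fits a logistic model with only an intercept, with subject as the repeated measure. The adjusted rate and its 97.5% one-sided lower limit come from that intercept, and the endpoint passes if the limit exceeds 88%. On the correlation it says: "An unstructured correlation matrix will be used, unless a different structure is found to be more appropriate".

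No posture weights are stated. No criterion, timing or fallback is given for changing the structure. The section refers to the SAP. SAP 1.1 introduces sample code and defines its variables, including the success indicator for each test in all postures, but the code is not in the supplied text and the surrounding prose gives no selection rule.

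The unadjusted Score limit, the tipping-point analysis and the posture poolability test at the 15% level are also planned. The last is meant "to determine whether there are differences among the four postures" (Protocol 11.6.3.1). None is given a role in the pass/fail decision.

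**The concern.** Protocol 11.5.1 makes study success depend on Safety Endpoint 1 and both primary effectiveness endpoints. Its control of overall error relies on each being tested at 2.5%. A rule for one of them that can run well above 2.5% weakens that argument.

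There are two separate problems. First, an unstructured matrix in an intercept-only model sets the posture weights from the data, so the quantity compared with 88% may not be the rate the protocol describes. The protocol expects posture to matter: section 6.6 says communication can be affected by how the devices are oriented to each other, which is why several postures are tested. Second, the structure of a test performed once can be changed on an unstated ground, possibly after the results are visible.

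**Working it through.** **The plan's own figure.** The inputs are in the Synopsis table ("95% 88% One-Sided Lower Pointwise Confidence Limit") and Protocol 11.1.4.2 (one-sided 2.5%, power 80%, attrition 30%).

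- n = [1.96·√(0.88·0.12) + 0.8416·√(0.95·0.05)]² / 0.07² = (0.6369 + 0.1834)² / 0.0049 = 137.3.
- With continuity correction: (137.3/4)·[1 + √(1 + 2/(137.3·0.07))]² = 151.3, so 152 tests = 4 × 38 subjects.
- Attrition: 38/0.7 = 54.3, so 55 subjects and 220 tests.

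The stated size reproduces, although the formula treats the 152 tests as independent.

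**The weighting.** I read the model as generalised estimating equations with a robust standard error. With only an intercept, every test has the same fitted mean μ and variance. With complete data the estimating equation is Σᵢ 1′R⁻¹(yᵢ − μ1) = 0, which gives

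μ = Σⱼ wⱼ·pⱼ, with w = R⁻¹1 / (1′R⁻¹1),

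where pⱼ is the observed rate in posture j and R the working correlation. The weights are all 0.25 only if the row sums of R are equal. That holds for independence (row sum 1) and exchangeable (1 + 3ρ), but not in general for unstructured.

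Two examples, each with a true average of 88% (weights as found by simulation with estimator B below):

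- 86/86/86/94%, best posture least correlated, weights 0.2/0.2/0.2/0.4: 0.6·86 + 0.4·94 = 89.2%.
- 92/92/92/76%, worst posture least correlated, same weights: 0.6·92 + 0.4·76 = 85.6%.

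The same mechanism therefore moves the estimate up or down.

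**Error rate at a true average of 88%.** The data are correlated binary results from a latent normal with four complete tests per subject. The lower limit is expit(b − 1.96·se), and a false pass is a limit above 88%. The numbers of subjects, 134 and 223, are the interim and final sizes in Protocol 11.1.1.2. The posture rates and correlations are assumed, because the documents give none. Estimator A uses a common dispersion with the diagonal set to 1. Estimator B rescales to a correlation matrix. The last row used 3,000 runs and the others 4,000 to 10,000. At 4,000 runs the Monte Carlo standard error at 2.5% is √(0.025·0.975/4000), about 0.25 points.

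| Posture rates (%), latent correlation | n=134, unstructured A / B | n=223, unstructured A / B | Independence, n=134; n=223 |
|---|---|---|---|
| 92/92/92/76, worst least correlated (0.8 vs 0.3) | 0.7 / 0.4 | 0.3 / 0.1 | 3.0; 2.7 |
| 88 in all, 0.5 | 3.6 / 3.4 | 2.9 / 2.5 | 2.7–3.1; 2.5 |
| 92/90/86/84, 0.5 | 5.4 / 4.0 | 4.9 / 3.4 | 2.8–3.0; 2.3 |
| 94/94/82/82, 0.5 | 9.9 / 4.8 | 12.0 / 4.5 | 2.9–3.1; 2.3–2.5 |
| 86/86/86/94, best least correlated (0.8 vs 0.3) | 11.9 / 9.4 | 16.7 / 11.9 | 2.5; 2.2 |
| 94/94/82/82, weak pair 0.85, others 0.3 | 12.0 / 10.5 | 19.5 / 16.1 | 2.5; 2.5 |

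A smaller spread, 91/89/87/85%, gave 2.8–3.5% with B and 3.3–4.0% with A (latent correlations 0.3 and 0.6). A shorter repeat of the 94/94/82/82%, 0.5 case gave 9.3/4.2% and 11.8/3.8%, so the low end there is nearer 4% with B.

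**Fit failures.** In the last row, estimator A gave a matrix that was not positive definite in about 27–33% of runs. The tabled figures count those runs as non-passes. Leaving them out raises 19.5% to 19.5/(1 − 0.27), about 27%. At the stated minimum of 38 subjects the unstructured fit failed in about 3–26% of data sets with A and 1–15% with B, depending on the scenario.

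**The swap.** Taking whichever structure passes added at most about 1 to 1.5 points where the unstructured test was at or above nominal. In the 92/92/92/76% case it brought the error back to about 2.4–3.0% at these sample sizes.

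**The case against.** The strongest reply is that the large figures rest on inputs the documents do not contain. They need a 12-point gap between posture pairs, or unequal correlations, or both. The protocol also programs the telemetry setting one unit above the highest threshold among the four postures at 1 month (10.3.4.5, 10.5.3.2), which should narrow posture differences at 6 months. The estimator and software are not named, and they alter the size and sometimes the direction: for 92/92/92/76% with equal latent correlations of 0.3 or 0.6, B gave 1.8–2.8% and A 3.3–9.7%. All of this stands, and it is why the figures are a range under assumptions.

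The SAP code may fix the structure, fallback and variance. Its absence from the supplied text is not a fault in the plan. Even so, the protocol's exception would still need closing.

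Protocol 11.7 requires changes made before analysis to be in an approved SAP and later ones to be reported. That is partial protection, since it does not require the data to be unseen. The Score limit and the posture-specific rates will also be shown, so a divergent adjusted rate would be visible, but they do not decide the endpoint.

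A reader might infer that the estimate is biased upward whenever postures differ. That is not supported: with the worst posture least correlated the test is conservative and the estimate falls to about 86%, and mild differences cost little. A reader might also infer that a later change of structure is the main source of error. It is not; most of the inflation comes from the unstructured weighting itself.

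**Conclusion.** The point holds as a should-fix. The structure is left open without a stated rule, and the default named in the protocol does not in general estimate the success rate over all posture tests. At a true average of 88% with 134 to 223 subjects, the false-pass rate runs from about 0.1–0.7%, through about 2.3–4% for equal or mildly different postures, to about 5–20% for the larger posture gaps. Independence stays at about 2–3%.

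Confidence is high that the clause is open and that the weighting follows. It is lower on size and direction, which depend on assumed posture rates, correlations and software. Fit failure in the extreme case makes a data-driven switch a realistic prospect. If true success is near the expected 95%, the choice may not change the outcome; it matters near the goal. The stated sample size is not in dispute.

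**What to change.** In Protocol 11.1.4.3, replace the sentence on the correlation matrix with: *An independence working correlation with empirical (sandwich) standard errors clustered on subject will be used; no other structure will be substituted for the primary test.* Align the code in SAP 1.1.

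With complete data the estimate is then the plain proportion of successful tests over the four postures, with a limit that allows for clustering. Keep the planned Score limit as a descriptive sensitivity analysis and note that it ignores clustering. Report any unstructured fit as sensitivity only. An exchangeable fit adds nothing with complete data, because it gives the same result as independence.

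The cost is one protocol sentence and one code option, with no added patients, visits or tests. The reported rate or limit may be slightly less favourable in some data sets.

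### Primary Effectiveness Endpoint 1: the planned sensitivity limit ignores clustering of posture tests within subject, so with positive correlation it is too high and adds little as a check on a pass

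*Protocol*

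**What the plan says.** Communication is tested once in each of four postures at the 6 Month Visit. Protocol 11.1.4 fixes the unit of analysis: "The test unit for this endpoint will be the result from each posture".

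Protocol 11.1.4.3 fits a logistic model with "subject as the repeated measure in an intercept only model" and compares its 97.5% one-sided lower limit with the 88% goal. On the correlation structure it says: "An unstructured correlation matrix will be used, unless a different structure is found to be more appropriate". It then plans the unadjusted rate with a 97.5% lower limit "using the one-sided Score methodology will also be presented as sensitivity analysis". That sentence is partly garbled, but the unadjusted rate and the Score method are clear, and no allowance for clustering is described.

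The other planned checks are a tipping point analysis for missing posture tests (11.1.4.3), a posture poolability test (11.6.3.1) and a subject-level summary of the number of successful postures (11.2). No interval or test is stated for that summary. SAP 1.1 describes code for the adjusted estimate only, and the code itself is not in the readable text.

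**The concern.** The main model accepts that tests from one subject may be alike. The sensitivity analysis drops that structure and puts a binomial limit on the tests as if each came from a different person.

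Positive correlation is plausible. All four tests in a subject use the same implanted device pair and the same programmed Telemetry Setting (Protocol 10.7.3.2). Under positive correlation the raw rate varies more than the binomial formula allows, so the Score limit sits too high and its 97.5% label is not accurate.

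What is at stake is how the result is read. A sensitivity analysis is useful if it can expose a fragile pass. A limit that nearly always lies above the main one will seem to confirm a pass whether or not the pass is robust. Near the goal it could also look like a pass beside a main analysis that failed.

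**Working it through.** **Inputs from the documents.** Goal 88%; expected rate 95%; one-sided 2.5%; power 80%; attrition 30%; four tests per subject (Protocol synopsis, 11.1.4 and 11.1.4.2). The analysis takes place when at least 134 subjects (interim) or 223 (final) have 6 months of follow-up (11.6.1.2).

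**Assumptions.** The documents give no ICC; 0 to 0.3 is assumed. The counts 134 and 223 belong to Safety Endpoint 1 and are used here as approximate numbers of subjects with four tests each.

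**1. The plan's own figure.** The plan states: "The required sample size of 152 tests from a minimum of 38 subjects (220 tests including attrition"). The normal approximation gives

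n = [(1.960·√(0.88·0.12) + 0.842·√(0.95·0.05)) / 0.07]² = [(0.6369 + 0.1834)/0.07]² = 137.3.

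With continuity correction, (n/4)·(1 + √(1 + 2/(0.07n)))² = 34.33 × 2.0991² = 151.3, so 152 tests, or 38 subjects. Then 38/0.7 = 54.3, so 55 subjects and 220 tests. The figures reproduce.

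**2. First-order effect of clustering.** With four tests per subject the design effect is DE = 1 + 3·ICC. The Score rule passes when (p̂ − 0.88)/√(0.88·0.12/N) exceeds 1.960, but the true standard deviation of p̂ is √DE times that denominator. The actual one-sided error is therefore about 1 − Φ(1.960/√DE):

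- ICC 0: DE 1.0, 1.960, 2.5%
- ICC 0.1: DE 1.3, 1.719, 4.3%
- ICC 0.2: DE 1.6, 1.549, 6.1%
- ICC 0.3: DE 1.9, 1.422, 7.8%

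**3. Simulation at a true rate of 88%** (beta-binomial, four tests per subject). Error of the Score rule:

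| ICC | 134 subjects | 223 subjects |
|---|---|---|
| 0 | 2.3% | 2.5% |
| 0.1 | 3.8% | 4.1% |
| 0.2 | 5.4% | 6.2% |
| 0.3 | 6.9% | 8.0% |

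Repeat runs move these by up to about 0.4 points. An intercept-only logistic limit with a subject-level robust variance, standing in for the planned model, stays at about 2.1% to 2.7% in the same cells.

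**4. Direction of disagreement.** With 134 or 223 subjects and ICC of 0.1 or more, the Score limit lies above the adjusted limit in 96% to 100% of runs. It fails in at most 0.6% of the runs where the adjusted limit passes. At ICC 0 the two limits agree on average.

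**5. Size at the expected rate.** The Score lower limit is [p̂ + z²/2n − z√(p̂(1−p̂)/n + z²/4n²)] / (1 + z²/n), with z = 1.960. Put p̂ = 95%, and n = tests divided by DE for the clustered version:

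| Subjects (tests) | Unadjusted | ICC 0.1 | ICC 0.3 | ICC 1 |
|---|---|---|---|---|
| 134 (536) | 92.8% | 92.5% | 91.8% | 89.9% |
| 223 (892) | 93.4% | 93.1% | 92.6% | 91.3% |

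Every entry clears 88%. In simulation at a true 95% with 134 subjects, the Score limit passes while the adjusted limit fails in about 0.1%, 0.6% and 1.6% of runs at ICC 0.1, 0.2 and 0.3. At a true 92% and ICC 0.2 this rises to about 16%.

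**6. Where the two rules split.** With 134 subjects and ICC 0.2, the smallest Score pass is 487/536 = 90.9%. At the effective size 536/1.6 = 335, the limit is 87.9% at 91.4% observed and 88.0% at 91.5%. The band of conflicting answers is about 90.9% to 91.5%.

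**The case against.** **No decision rests on this limit.** Only the adjusted limit is compared with 88%. A reader might infer from the error rates above that the trial's type I error is inflated. The documents do not support that: the adjusted rule allows for clustering and holds its level. This stands in full.

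**The correlation is not known.** Protocol 6.6 says communication depends on the relative orientation of the devices, which is why posture is varied, so some failures may be specific to a posture. At ICC 0 the Score limit is correct, and with negative correlation it would be too low. This stands: the point is conditional.

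**It is not useless.** A reader might conclude that the Score limit cannot check the main result at all. That goes too far. The gap between the two limits shows how much clustering matters. At the 38-subject minimum with ICC 0 or 0.1, the Score limit fails in 0.3% to 23% of the runs that pass the main analysis. With 134 or more subjects and ICC of at least 0.1, that ability nearly vanishes.

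**Other checks exist.** The tipping point analysis, the poolability test and the subject-level summary are all planned. None of them gives a second interval that respects clustering.

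**A bootstrap would track the main result.** With 134 to 223 subjects it should lie close to a robust-variance limit, so it is not a fully independent challenge. That is fair, but it does not depend on the working correlation, which the plan leaves open to change.

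**Conclusion.** The point holds as a minor one. In the readable text, the only alternative interval for this endpoint ignores clustering. Over an assumed ICC of 0.1 to 0.3, its one-sided error at a true 88% is about 3.8% to 6.9% with 134 subjects and 4.1% to 8.0% with 223. At ICC 0 it is close to the nominal 2.5%. Under positive correlation the 97.5% label is therefore not accurate, and the limit adds little as a check on a pass.

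The result rests on an assumed ICC, on beta-binomial data with four complete tests per subject, and on Safety Endpoint 1 counts. The practical effect is small if success is near the expected 95%; it matters only if the observed rate falls much closer to the goal. Nothing here shows that the endpoint could be wrongly passed under the prespecified rule, and nothing here is a finding against the sample size.

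**What to change.** Keep the unadjusted rate, and replace the Score limit in Protocol 11.1.4.3 or the SAP with one that keeps the subject as the unit. One suitable form is a subject-level bootstrap: resample subjects with replacement, keep all tests of a subject together, recompute the raw rate, and take the 2.5th percentile as the lower limit. State the number of resamples and the seed in advance.

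If the sponsor prefers no second interval, show the unadjusted rate without an inferential limit.

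The cost is one sentence and a few lines of code. No new data are needed, and the sample size and decision rule do not change. The downside is that the sensitivity limit becomes slightly less favourable: by the table in step 5, about 0.3 points at ICC 0.1 and 1.0 point at ICC 0.3 with 134 subjects and 95% observed.
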